## 5. STATISTICS

Three cohorts of patients will be prospectively included in the study (Figure 1 in the Appendix):

**1) Letrozole-stimulated cohort:** this includes all newly diagnosed breast cancer who are candidates to receive (neo)adjuvant chemotherapy and undergo oocyte/embryo cryopreservation at the Belgian participating centres.

**2) Standard-stimulated cohort:** this includes all newly diagnosed breast cancer who are candidates to receive (neo)adjuvant chemotherapy and undergo oocyte/embryo cryopreservation at the French participating centres.

**3) Non-stimulated cohort:** this includes all newly diagnosed breast cancer who are candidates to receive (neo)adjuvant chemotherapy who have access to the Fertility Clinics in all the participating centres but are not willing to undergo oocyte/embryo cryopreservation. Patient who underwent another fertility preservation procedure (ovarian tissue cryopreservation, GnRH analogues,...) are eligible in this cohort.

All the efficacy analyses will be performed to compare the letrozole-stimulated cohort and the standard-stimulated cohort. All the safety analyses will be conducted to compare separately the letrozole-stimulated cohort with the non-stimulated cohort and the standard-stimulated cohort with the non-stimulated cohort.

To evaluate the efficacy of performing a controlled ovarian stimulation with or without letrozole in young women with newly diagnosed breast cancer who are candidates to receive (neo)adjuvant chemotherapy, the following endpoints will be assessed:

- Number of mature oocytes collected (primary endpoint).
- Number of oocytes collected;
- Maturation rate: defined as ratio between the number of mature oocyte collected and total number of oocyte collected;
- Number of oocyte/embryo cryopreserved;
- Number of patients with poor response: defined as retrieval of  $\leq 4$  oocytes;
- Number of patients with stimulation failure: defined as no follicular growth after 1 week of adequate controlled ovarian stimulation administration.

The efficacy of performing controlled ovarian stimulation with or without letrozole will be evaluated also in various subgroups of young women with newly diagnosed breast cancer who are candidates to receive (neo)adjuvant chemotherapy according to the following characteristics:

- Type of stimulation: follicular vs. random;
- Hormone receptor status: positive vs. negative;
- Presence of *BRCA* mutation: *BRCA*-mutated vs. *BRCA*-not mutated.

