To evaluate the safety of performing a controlled ovarian stimulation with or without letrozole in young women with newly diagnosed breast cancer who are candidates to receive (neo)adjuvant chemotherapy, the following endpoints will be assessed:

- Invasive disease-free survival (iDFS) defined as the time from study inclusion to the first appearance of the following invasive events: local recurrence, distant metastases, contralateral or ipsilateral breast tumor, second primary malignancy, or death from any cause;
- Breast cancer-free interval (BCFI) defined as the time from study inclusion to the first appearance of the following invasive events: local recurrence, distant metastases, contralateral or ipsilateral breast tumor;
- Overall survival (OS) defined as the time from study inclusion to death from any cause;
- Kinetic of circulating tumor DNA (ctDNA) assessed before, after stimulation and during study follow-up (if disease relapse).
- Complications associated with any of the procedure used for oocyte/embryo cryopreservation.

The safety of performing controlled ovarian stimulation with or without letrozole will be evaluated in various subgroups of young women with newly diagnosed breast cancer who are candidates to receive (neo)adjuvant chemotherapy according to the following characteristics:

- Stage at diagnosis: I vs. II vs. III;
- Hormone receptor status: positive vs. negative;
- HER2 status: positive vs. negative;
- Type of exposure to chemotherapy: prior to surgery (neoadjuvant) vs. post surgery (adjuvant);
- Exposure to endocrine therapy: exposure vs. no exposure;
- Presence of *BRCA* mutation: *BRCA*-mutated vs. *BRCA*-not mutated;
- Baseline ctDNA level: present vs. absent.

The following baseline characteristics of young women with newly diagnosed breast cancer who undergo controlled ovarian stimulation with or without letrozole will be assessed:

- Body-Mass Index (BMI) and body surface;
- Smoking history;
- Age at menarche;
- Prior pregnancies (completed, induced or spontaneous abortion);
- Prior treatment for infertility;
- Prior use of birth control pills;
- Prior gynecological diseases with potential impact on reproductive potential;
- Baseline ovarian reserve and function analysis.

Furthermore, the following characteristics of protocols with or without letrozole used for controlled ovarian stimulation in young women with newly diagnosed breast cancer who are candidates to receive (neo)adjuvant chemotherapy will be evaluated:

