The impact of anticancer therapies on patients' ovarian function will be evaluated in various subgroups of young breast cancer patients according to:

- Age: <30 vs. 30-35 vs. > 35;
- Type of chemotherapy received: anthracycline- and taxane-based vs. taxane-based vs. others;
- Number of months of chemotherapy received: <4 months vs. > 4 months;
- Exposure to platinum agents: use vs. no use.
- Exposure to endocrine therapy: use vs. no use.
- Exposure to anti-HER2 therapy: use vs. no use.
- Presence of *BRCA* mutation: *BRCA*-mutated vs. *BRCA*-not mutated.

The sample size has been estimated based on the study primary endpoint (i.e. number of mature oocytes collected). With 113 patients in the standard-stimulated cohort and 113 in the letrozole-stimulated cohort, assuming a mean number of mature oocytes collected of 6.1 in the standard-stimulated cohort, the study will have a power of 0.80 to reject the null hypothesis of equal means when the population mean difference is 1.5 mature oocytes collected (estimating a mean number of mature oocytes collected of 7.6 in the letrozole-stimulated cohort) with a standard deviation for both groups of 4.0 and with a significance level (alpha) of 0.05 using a two-sided two-sample equal-variance t-test. Considering that approximately one out of three (1:3) eligible patients counseled to

undergo controlled ovarian stimulation for oocyte cryopreservation before starting anticancer treatments will accept the procedure, it is estimated to enroll 339 patients in the non-stimulated cohort.

Patients demographic, clinical and pathologic baseline characteristics will be compared in the three cohorts using chi-square test or Fisher Exact test for categorical variables and Wilcoxon rank-sum test or t-test for continuous variables, as appropriate.

Dicothomous outcomes will be compared using univariate and multivariate logistic regression models. Time-to-event outcomes will be estimated and plotted using Kaplan-Meier methods. Survival rates will be compared using log-rank test and Cox proportional hazards models for univariate and multivariate analysis, respectively.

All tests will be two-sided and p-values of  $< 0.05$  will be considered statistically significant.

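### Subgroup safety analyses fall under a blanket p<0.05 significance rule, with no heterogeneity test, multiplicity rule or exploratory label specified

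*Combined protocol and SAP*

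**What the plan says.** All of the relevant text is in Section 5 (Statistics).

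- **Contrasts.** Safety is compared twice: letrozole-stimulated against non-stimulated, and standard-stimulated against non-stimulated.
- **Safety endpoints.** Three are time-to-event: iDFS, BCFI and OS. ctDNA kinetics and procedure complications are also listed.
- **Safety subgroups.** "The safety of performing controlled ovarian stimulation with or without letrozole will be evaluated in various subgroups". The factors are stage (three levels) and six two-level factors: hormone receptor status, HER2, chemotherapy timing, endocrine therapy exposure, BRCA mutation and baseline ctDNA.
- **Efficacy subgroups.** "The efficacy of performing controlled ovarian stimulation with or without letrozole will be evaluated also in various subgroups". There are three two-level factors.
- **Ovarian-function subgroups.** Seven further factors are listed.
- **Methods.** Log-rank and Cox for survival; univariate and multivariate logistic models for dichotomous outcomes. The terms of the multivariate models are not given.
- **Decision rule.** "All tests will be two-sided", and any p-value below 0.05 counts as statistically significant. No exception is made for subgroups.

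The sample size rests on the number of mature oocytes alone. No subgroup or survival comparison is sized.

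**The concern.** Two problems follow from applying the stated rule to the listed subgroups.

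First, many comparisons share a 5% threshold, so some will cross it by chance. The rule would then call each of them a significant safety finding.

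Second, a within-level test does not answer the subgroup question. A p-value below 0.05 in BRCA-mutated women and above 0.05 in the others does not show that the two effects differ. Likewise, a non-significant result in a small stratum is not reassurance.

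The stakes are practical. Section 1 says the study should improve oncofertility counselling, and a chance result in receptor-positive or BRCA-mutated women could change what patients are told. Section 1 also cites subgroup p-values by BRCA and receptor status from the earlier single-centre safety study, and cautions that its numbers were limited. The study's own plan carries no such caution.

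**Working it through.** **1. The plan's own figure.** Section 5 states that "the study will have a power of 0.80 to reject the null hypothesis of equal means" with 113 per stimulated cohort, "when the population mean difference is 1.5 mature oocytes collected", "with a standard deviation for both groups of 4.0" and "with a significance level (alpha) of 0.05 using a two-sided two-sample equal-variance t-test".

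- Normal approximation: n = 2 x (1.960 + 0.842)² x (4.0/1.5)² = 111.6, so 112 per cohort.
- Exact two-sample t-test: n = 112.6, so 113 per cohort, with power 0.801.

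The figure is reproduced. It covers the primary endpoint only. The plan gives no number of subgroup tests and no error rate for them.

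**2. Count of survival subgroup tests.**

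- Levels: 3 + 6 x 2 = 15.
- Tests, if one is run per level: 15 levels x 3 endpoints x 2 contrasts = 90.
- If both a log-rank and a Cox p-value are reported: 180.

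ctDNA kinetics and complications are not counted.

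**3. Expected chance findings with no true effect.**

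- 90 x 0.05 = 4.5. This needs each test to hold its 5% level but does not need independence.
- Nominally towards harm: 90 x 0.025 = 2.25.

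**4. Chance of at least one.**

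- If independent: 1 - 0.95^90 = 0.99. Towards harm: 1 - 0.975^90 = 0.90.
- Independence fails. iDFS and BCFI share most event types, death counts in both iDFS and OS, both contrasts use the same non-stimulated cohort, and the same women recur under all seven factors.

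A null simulation kept these overlaps: cohorts of 113, 113 and 339, a log-rank test in every level, five years of follow-up and 1,500 replicates per row. The documents give no event risks or prevalences, so these are assumptions: stage split 30/50/20%, receptor-positive 65%, HER2-positive 25%, neoadjuvant 50%, BRCA-mutated 15%, ctDNA present 30%, and endocrine therapy matching receptor status in 95%.

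| Assumed 5-year recurrence risk | Mean false positives | At least one | Mean towards harm | At least one towards harm |
|---|---|---|---|---|
| 10% | 4.05 | 75% | 2.98 | 56% |
| 15% | 4.10 | 79% | 2.72 | 58% |
| 25% | 4.48 | 80% | 2.88 | 56% |

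The simulated share towards harm is 64% to 73%, above the nominal half. A likely reason is skew of the log-rank statistic when events are few and the stimulated cohort is a quarter of each contrast (113/452).

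**5. Efficacy subgroups.** 3 factors x 2 levels x 6 endpoints = 36 comparisons, and 36 x 0.05 = 1.8. This count is less secure. Four of the six endpoints are counts or a ratio, and the only comparison method given for such outcomes is the t-test in the sample-size sentence.

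**6. Effect of moving to interaction tests.**

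- All seven factors: 7 x 3 x 2 = 42 tests; 42 x 0.05 = 2.1 expected false positives; 1 - 0.95^42 = 0.88 for at least one if independent.
- Without endocrine therapy exposure: 6 x 3 x 2 = 36 tests; 36 x 0.05 = 1.8; 1 - 0.95^36 = 0.84 if independent.

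Interaction tests more than halve the count and ask the right question, but they do not remove chance findings.

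**7. Power of interaction tests.** If the overall log hazard ratio has variance V, each of two equal halves has variance 2V, and the difference between them has variance 2V + 2V = 4V. Heterogeneity is therefore hard to detect.

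**The case against.** The case on the other side has several parts.

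- **The plan does not prescribe within-level tests.** A reader might infer that 90 p-values are planned. The text says only that safety will be evaluated in subgroups. This stands: 90 is conditional on applying the named survival tests in each level.
- **Heterogeneity might still be tested.** A reader might infer that it is excluded. The multivariate models are left open and could hold an interaction term. This stands: the supportable statement is that no such test is specified.
- **The 99% figure.** A reader might infer that a false signal is nearly certain. That needs independence, which clearly fails. This stands.
- **Direction.** A reader might take all 4.5 chance findings as safety alarms. The tests are two-sided, and nominally half would favour stimulation. This stands.
- **Non-randomised cohorts.** They are formed by country and by patient choice, so chance is not the only source of error. True, but confounding adds to the problem and does not excuse the rule.
- **Prespecified, secondary analyses.** The factors and levels are fixed in advance, safety is a secondary objective, and the primary analysis is untouched. This limits post hoc selection and the seriousness of the point. It does not change how a chance p-value below 0.05 would be labelled.
- **Overall safety tests.** A reader might conclude that significance should be reserved for the primary endpoint. That would also strip the overall iDFS, BCFI and OS comparisons, where this point shows no fault.

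**Conclusion.** The concern holds in limited form. The counts of levels, endpoints and contrasts come directly from Section 5, and so does the unqualified significance rule. If the named tests are run in each level, about 4.5 of 90 results would be called significant with no true effect, nominally half of them towards harm. The chance of at least one is about 75% to 80%, and 56% to 58% for at least one towards harm. Those percentages rest on assumed event risks and prevalences and on cohorts that differ only by chance.

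This is more than a missing detail, because following the rule as written would label chance subgroup results as significant safety findings. The plan should be changed, but the primary comparison and its sample size are not affected.

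**What to change.** Amend Section 5, and the matching statistics text in the Synopsis, as follows.

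1. For each baseline subgroup factor, fit one cohort-by-factor interaction term in the Cox model for each survival endpoint and contrast, with a joint test for the three stage levels. Do the same in whatever model is used for each efficacy endpoint, and name that model.
2. Report level-specific estimates with 95% confidence intervals, for example in a forest plot.
3. Label all subgroup results exploratory and state that the p<0.05 sentence does not apply to them, including the ovarian-function subgroups. With no significance claims, no alpha adjustment is needed.
4. Leave the overall iDFS, BCFI and OS comparisons unchanged.
5. Do not enter endocrine therapy exposure as a plain baseline factor in this analysis. Survival time starts at inclusion and the exposure arises later.
6. State that a non-significant interaction is not evidence of equal effects.

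The cost is SAP wording and one interaction per factor in each model, with no new data or patients. The downside is that fewer results can be called significant and that interaction tests have low power.

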### 3.2. Data collection

For all consecutive eligible patients included in the study, anonymized data will be entered into ad hoc electronic Case Report Forms (eCRF). The following information will be collected:

1) Baseline characteristics (at study inclusion): BMI; smoking habit; age at menarche; use of birth control pills; prior children before breast cancer diagnosis; history of spontaneous or induced abortion; prior treatment for infertility; prior gynecological surgery and/or medical history with possible impact on fertility; baseline AMH value.

- 2) Breast cancer history: date of diagnosis; age at diagnosis; disease stage; type of breast and axillary surgery; histology; tumor size and nodal status (for patients who underwent primary systemic therapy, both clinical tumor size and nodal status before treatment initiation and pathological tumor size and nodal status at the time of surgery will be collected); grade; hormone receptor status (estrogen and progesterone receptors); HER2 status.
- 3) Treatment of the primary tumor: timing of systemic therapy administration (adjuvant or neoadjuvant); use of chemotherapy (type and number of cycles); use of endocrine therapy (type and duration); use of anti-HER2 targeted therapy (type and duration); use of radiotherapy; use of breast reconstruction surgery.
- 4) Survival status: any recurrence of invasive breast cancer including date of the event; type of recurrence of invasive breast cancer (locoregional or distant event); any second primary contralateral breast cancer including date of the event; any second primary malignancy including date of the event; date of last follow-up and/or death.
- 5) Controlled ovarian stimulation protocol: type of stimulation (follicular or random); total FSH dose; number of stimulation days; number of days with antagonist; estradiol and progesterone levels at triggering and during luteal phase (L3-L8); number of oocyte/embryo collected; number of mature oocytes collected; maturation rate; number of oocyte/embryo cryopreserved; number of patients with poor response; number of patients with stimulation failure.
- 6) Ovarian function before and after chemotherapy: treatment-induced amenorrhea; age at menopause; AMH values.
- 7) Pregnancy after breast cancer: any pregnancy including date of the event; pregnancy outcome; gestational age at delivery; pregnancy/fetal/obstetrical outcomes; breastfeeding and its duration; use and type of assisted reproductive technology.

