**Table 1. Schedule of assessment for correlative research**

	Inclusion (diagnosis)	M 0-1 (start of COS)	M 0-1 (end of COS)	M4-6 (end of CT)	M 16-18 (12 M after CT)	M 28-30 (24 M after CT)	M 60 (5 y after diagnosis)	Relapse
Serum (AMH, FSH, E2)	x			x	x	x	x	
Serum (Progesterone/E2)		x*	x**					
Plasma for ctDNA	x		x					x
Whole blood	x							
1 block of FFPE of primary tumor s	x							

x: mandatory

\$: 15 representative slides of 10 µm should be provided.

\*: Can be performed at the inclusion if COS start within 5days

\*\* : serum samples at L3 and L8 will be collected

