#### **4.4. Laboratory procedures for circulating tumor DNA**

Three blood samples of 10 ml should be collected in EDTA tubes; two samples will be centrifuged within 1 hour from collection, to separate plasma from peripheral blood cells, at 820g for 10 minutes at  $4^{\circ}\text{C}$ . Recover and transfer plasma (the top yellowish layer of the tube content) into new micro tubes, compatible with high-speed centrifuge. Centrifuge the plasma at maximum speed (if available 20000g is recommended) for 10 minutes at  $4^{\circ}\text{C}$ . Transfer all plasma into cryovials and stored at  $-80^{\circ}$ . The 3rd sample of whole blood will be stored directly at  $-80^{\circ}\text{C}$ . Blood and plasma samples will be shipped on dry ice to the central laboratory (Erasmus hospital) at fixed time points for evaluation.

Plasma samples will be collected at enrollment (i.e. at the time of oncofertility counseling/breast cancer diagnosis) before starting chemotherapy (and before starting controlled ovarian stimulation in patients who access oocyte/embryo cryopreservation), Then, this analysis will be repeated at the end of controlled ovarian stimulation, and at relapse or end of follow-up.

In this study, evaluation of the circulating tumor DNA (ctDNA) in the plasma will be performed. The aim is to 1) evaluate the effect of controlled ovarian stimulation on the levels of ctDNA and correlate

with risk of recurrence and 2) to evaluate the pattern of somatic mutations in young breast cancer patients.

Before performing the evaluation of ctDNA, primary tumor analysis is required. Hence, 15 representative slides (10µm) must be collected instead. Samples will be shipped to the central laboratory (Erasmus hospital) at fixed time points for evaluation.

The aim is to elucidate the biology of breast cancer in young women. Techniques will comprise but not restricted to immunohistochemistry, in situ hybridization, expression profiling and sequencing. Extraction of nucleic acids (DNA and RNA) may be required to perform these analyses.

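### The endocrine-therapy safety subgroup is defined by treatment that starts after time zero, so early recurrences in receptor-positive women move from the exposed to the unexposed stratum

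*Combined protocol and SAP*

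**What the plan says.** - **Subgroup.** Section 5 lists, among seven safety subgroups, "Exposure to endocrine therapy: exposure vs. no exposure". It gives no time point, landmark or definition by intended treatment.
- **Time zero.** iDFS and BCFI are the "time from study inclusion to the first appearance of the following invasive events". The third endpoint reads "Overall survival (OS) defined as the time from study inclusion to death from any cause".
- **When inclusion happens.** Section 4.4 places the baseline sample "at enrollment (i.e. at the time of oncofertility counseling/breast cancer diagnosis) before starting chemotherapy", and before any stimulation. Table 1 puts the end of chemotherapy at months 4 to 6. Its last scheduled visit is "M 60 (5 y after diagnosis").
- **Method.** "Survival rates will be compared using log-rank test and Cox proportional hazards models for univariate and multivariate analysis, respectively". Kaplan-Meier curves are also planned. No time-dependent covariate is mentioned.
- **Contrast.** Section 5 compares each stimulated cohort separately with the non-stimulated cohort in all safety analyses.
- **Data.** Section 3.2 lists "use of endocrine therapy (type and duration"). A start date is not listed.
- **Baseline alternative.** Hormone receptor status, positive or negative, is already a separate safety subgroup in Section 5.

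**The concern.** Follow-up begins before chemotherapy, and a woman's endocrine status is settled only afterwards. If she relapses or dies first, an ever/never rule places her in the unexposed stratum even if her tumour is receptor-positive. The exposed stratum then carries a stretch of follow-up in which, by construction, nobody can have an event. The outcome helps to decide the subgroup.

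Section 1 says why this matters here: the fear is that the high-estrogen state of stimulation promotes growth or recurrence, particularly in endocrine-sensitive disease. Early harm of that kind would be understated in the exposed stratum and would appear in the unexposed stratum, which should consist mainly of receptor-negative women.

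**Working it through.** **The plan's own figure.** There is none for this subgroup: no event rate, hazard ratio or power is stated for any safety endpoint. The 113 per stimulated cohort reproduces (difference 1.5, SD 4.0, two-sided 0.05: power 0.801), but it concerns oocyte number only.

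**Inputs.** From the documents: time zero at inclusion, a 60-month horizon, and cohorts of 113 and 339. Assumed, because the documents do not give them: 70% receptor-positive; 15% events at 5 years at a constant hazard; endocrine start at months 6-9 (7.5 used below); all event-free receptor-positive women start, unless stated otherwise.

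**1. Events before the start.** Monthly hazard λ = −ln(0.85)/60 = 0.00271. P(event before month 7.5) = 1 − exp(−7.5λ) = 0.0201. As a share of 5-year events this is 0.0201/0.15 = 13.4% (10.7% for a start at month 6, 16.1% at month 9). In 565 women: 565 × 0.70 × 0.0201 = about 8 events; in one cohort of 113, about 1.6.

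**2. Curves with no effect of anything.**
- Exposed, event-free at 5 years: 0.85/(1 − 0.0201) = 86.7%, against a true 85.0%.
- Unexposed: size 0.30 + 0.70 × 0.0201 = 0.3141; events 0.30 × 0.15 + 0.0141 = 0.0591; event-free 1 − 0.0591/0.3141 = 81.2%.

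**3. Planned contrast with no effect and equal uptake.** Both cohorts are filtered alike, so the HR is 1.0 in each stratum. Simulation confirms this.

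**4. Stimulation doubles the hazard for 12 months, in receptor-positive women only** (ratios of cumulative hazard).
- All receptor-positive women: (60 + 12)/60 = 1.20.
- Exposed, followed from month 7.5: (52.5 + 4.5)/52.5 = 1.09.
- Unexposed, stimulated: early events 0.70 × (1 − exp(−15λ)) = 0.70 × 0.0398 = 0.0279; risk (0.045 + 0.0279)/(0.30 + 0.0279) = 0.222. Non-stimulated risk, from step 2: 0.188. Ratio: ln(1 − 0.222)/ln(1 − 0.188) = 1.21.
- Receptor-negative women: 1.00 by construction.

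Cox models on simulated data, with uptake of 85-100%, give 1.21-1.22, 1.09-1.10 and 1.21-1.22 respectively.

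**5. The doubling lasts all 5 years.** Simulated HR: 2.00 in receptor-positive women, 2.00 in the exposed, and about 1.2 (full uptake) to 1.3 (90% uptake) in the unexposed. With incomplete uptake, part of that last figure is a real effect in receptor-positive women who never start.

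**6. No effect, but uptake of 75% in one cohort and 90% in the other.**
- Unexposed risk at 75%: (0.15 × 0.475 + 0.70 × 0.75 × 0.0201)/(0.475 + 0.0106) = 0.168.
- At 90%: (0.15 × 0.37 + 0.70 × 0.90 × 0.0201)/(0.37 + 0.0127) = 0.178.
- Ratio of cumulative hazards: 0.94, or about 1.06-1.07 with the gap reversed.

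**7. Precision.** Receptor-positive events: 113 × 0.70 × 0.15 = 11.9 against 339 × 0.70 × 0.15 = 35.6. SE of log HR = √(1/11.9 + 1/35.6) = 0.34, so a 95% interval is the estimate multiplied or divided by about 1.9. The shift from 1.22 to 1.09 is ln(1.22/1.09)/0.34 = about 0.3 SE.

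**The case against.** The strongest reply is that the plan never compares exposed with unexposed women. It compares cohorts within a stratum, where the event-free waiting period is common to both. That stands for the null case with equal uptake (step 3). It does not stand once stimulation affects early recurrence, which is the case a safety analysis has to serve. Nor is equal uptake assured, since the cohorts differ by country and by patient choice.

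Four stronger readings are tempting, and the documents do not support them.

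- **That the planned hazard ratio is biased to about 0.66.** That is the simulated exposed-against-unexposed HR under the null with full uptake. Section 5 plans no such contrast, so the figure warns only against reading across strata.
- **That the subgroup would hide harm in general.** The dilution among the exposed needs harm that is largely over soon after endocrine therapy starts. Section 1 gives no time window for the feared effect, and a lasting effect shows in full (step 5). The receptor-status subgroup would show either pattern.
- **That unequal uptake alone creates large false signals.** Figures of 0.62 and 1.60 arise if the unexposed stratum is limited to receptor-positive women, with an assumed 4% yearly hazard and a start at month 9. The stratum as written also holds the receptor-negative women, and step 6 then gives about 0.94 to 1.07.
- **That the start date is certainly not collected.** Section 3.2 is a summary list and the eCRF is not among the documents. Duration may be captured through dates.

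It also stands that the shifts are small beside this study's precision (step 7), and that this is one of seven secondary subgroups.

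**Conclusion.** The point holds in limited form. As written, the subgroup conditions on the future: the exposed curves are too favourable, and early receptor-positive events are counted as unexposed. The planned cohort contrast is unbiased with no effect and equal uptake. It is distorted if stimulation raises recurrence in receptor-positive women: with a 12-month doubling, about 1.22 becomes about 1.09 among the exposed, and about 1.2 appears among the unexposed where the receptor-negative value is 1.0. Unequal uptake adds a smaller distortion.

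The sizes rest on the assumed receptor-positive share, event rate, start time and uptake. The documents do not say when endocrine therapy starts; that it follows chemotherapy is an assumption, although inclusion at diagnosis puts any start after time zero. Few early events are expected. For OS the effect is smaller and indirect, mainly through women who relapse early and never start therapy for the primary tumour. The primary endpoint is untouched.

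**What to change.** Drop endocrine exposure as a safety subgroup measured from inclusion, and rely on the baseline hormone receptor subgroup already in Section 5.

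If exposure is still wanted, state one of two analyses in Section 5: a landmark (for example the end of chemotherapy, among women event-free at that point, classified by status then and followed from then), or endocrine therapy as a time-dependent covariate in the Cox model. Either needs the start date, so confirm that the eCRF captures it and add it to Section 3.2.

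The cost is a change of SAP wording, at most one date field, and, for a landmark, the few events that precede it. Treatment is not affected.

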8) Presence of germline *BRCA* mutation or other type of germline mutations (if available): date of genetic testing; type of mutation; use and date of breast prophylactic surgery; use and date of gynecological prophylactic surgery.

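### The BRCA safety subgroup has no cut-off for the test date and no class for untested women, so a test done after an event can decide which subgroup that event counts in.

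*Combined protocol and SAP*

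**What the plan says.** Section 5 lists seven subgroup factors for the safety endpoints. One is "Presence of *BRCA* mutation: *BRCA*-mutated vs. *BRCA*-not mutated". It has two classes and no time anchor, whereas stage is taken at diagnosis and ctDNA at baseline in the same list.

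Section 3.2, item 8, is the only source of the status: "mutation or other type of germline mutations (if available): date of genetic testing; type of mutation". It sets no latest date for the test. The item is separate from item 1, which is the group fixed at study inclusion. Table 1 and Section 4 schedule no germline BRCA test. Whole blood is stored at inclusion, but no BRCA test on it is described.

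The time-to-event endpoints all start at inclusion:
- "Invasive disease-free survival (iDFS) defined as the time from study inclusion to the first appearance of the following invasive events"
- "Breast cancer-free interval (BCFI) defined as the time from study inclusion to the first appearance of the following invasive events"
- "Overall survival (OS) defined as the time from study inclusion to death from any cause"

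On the comparison, Section 5 states "All the safety analyses will be conducted to compare separately the letrozole-stimulated cohort with the non-stimulated cohort", and likewise for the standard-stimulated cohort. On method, it states "Survival rates will be compared using log-rank test and Cox proportional hazards models for univariate and multivariate analysis, respectively". It gives no landmark, no delayed entry and no rule for women whose BRCA status is unknown, and it does not use the recorded test date.

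**The concern.** A woman's germline status is fixed, but whether it is known is not. Take two carriers, neither tested at diagnosis. One stays event-free, is never tested, and has no defined place in the subgroup. The other relapses in year 2, is tested because of it, and joins the mutated class with her event and all her follow-up from inclusion. Among women untested at diagnosis, those with an event are then more likely to reach a tested class than those without.

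This would have two effects. Event rates for iDFS and BCFI in the tested classes would be too high. In addition, if one cohort had fewer women tested at diagnosis, more of its women would enter through an event, and the within-subgroup comparison with the non-stimulated cohort would be distorted. Safety in carriers matters for counselling: Section 1 cites an earlier BRCA subgroup result as apparently reassuring, while noting that the numbers were limited.

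**Working it through.** **The plan's own figure.** The only sample-size calculation is for oocyte yield: difference 1.5, SD 4.0, two-sided alpha 0.05, 113 per stimulated cohort. An exact two-sample t-test gives power 0.801, so it reproduces. It does not bear on this point. The plan gives no figure for BRCA or for any survival endpoint.

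**Inputs.** From Section 5: 113 women per stimulated cohort and 339 non-stimulated. Assumed, because the documents give none:
- five-year event risk p = 15%;
- carriers 15%;
- no effect of stimulation or mutation;
- share tested at diagnosis t;
- share r of relapsing untested women who are then tested, 50% to 90%.

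**Risk in a tested class.** Women enter because they were tested at diagnosis, or because they had an event and were tested afterwards:

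risk(t) = p[t + (1 − t)r] / [t + (1 − t)pr]

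**Stimulated 90% tested, non-stimulated 70% tested:**
- r = 0.5: stimulated 0.1425/0.9075 = 15.7%; non-stimulated 0.1275/0.7225 = 17.6%. Hazard ratio = ln(1 − 0.1570)/ln(1 − 0.1765) = 0.1708/0.1942 = 0.88.
- r = 0.9: stimulated 0.1485/0.9135 = 16.3%; non-stimulated 0.1455/0.7405 = 19.6%. Hazard ratio = 0.1774/0.2188 = 0.81.

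A simulation with 1,000,000 women per cohort gave 0.89 and 0.82, which agrees.

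**Other settings, same formula, true hazard ratio 1:**

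| Tested at diagnosis, stimulated vs non-stimulated | r = 0.5 | r = 0.9 |
|---|---|---|
| 95% vs 85% | 0.95 | 0.91 |
| 90% vs 70% | 0.88 | 0.81 |
| 90% vs 60% | 0.81 | 0.71 |
| equal | 1.00 | 1.00 |
| 70% vs 90% (reversed) | 1.14 | 1.23 |

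With r = 0.1, the 90% vs 70% case gives only 0.97. With equal testing the contrast is unbiased, but the level is still raised: at 80% tested and r = 0.5, both cohorts show 16.6% instead of 15%.

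**Classing by baseline tests only.** In a separate Cox simulation (60,000 women, true hazard ratio 1), using only status known at inclusion gave hazard ratios of 0.97 to 1.02. The subgroup risks were 14-15%, against the true 15%.

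**Scale in this study (90% vs 70%).**
- Carriers: 113 × 0.15 = 17 stimulated; 339 × 0.15 = 51 non-stimulated.
- Carriers who enter through an event: 16.95 × 0.15 × 0.10 × r = 0.1 to 0.2 stimulated; 50.85 × 0.15 × 0.30 × r = 1.1 to 2.1 non-stimulated.
- Events among known carriers: 16.95 × 0.15 × (0.9 + 0.1r) = 2.4 to 2.5, against 50.85 × 0.15 × (0.7 + 0.3r) = 6.5 to 7.4.
- SE of the log hazard ratio: √(1/2.42 + 1/6.48) = 0.75, down to √(1/2.52 + 1/7.40) = 0.73. The 95% interval spans a factor of about 4.2 to 4.4 either way.
- Bias in SE units: |ln 0.88|/0.75 = 0.17, up to |ln 0.81|/0.73 = 0.29.

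**The case against.** The strongest reply is that the documents do not say that relapse prompts testing, that cohorts differ in testing, or how many women are tested. All cohorts are aged 40 or under at diagnosis, counselled on fertility preservation and candidates for chemotherapy, so testing may well be similar. This stands. The size is unknown, and the bias in the stimulation contrast is conditional. Different testing remains plausible, because the cohorts are formed by country and by patient choice, but it is not documented.

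The second reply is scale. With about 17 and 51 carriers, the contrast could not support a safety conclusion with or without a cut-off, and the shift is well under a third of a standard error. This also stands, and limits the point to a secondary subgroup in a study powered only for oocyte yield.

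A reader might also infer three things that the text does not support:
- That untested women will be counted as not mutated. Section 5 does not say so; leaving them out as missing is at least as natural. The fault is that the plan does not choose.
- That negative results are not recorded. Section 3.2 asks for presence of a mutation and a test date, which can already separate tested-negative from untested women, and the eCRF is not in the documents.
- That OS is distorted to the same degree. A woman tested at relapse has not necessarily died, and no OS figure was computed.

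None of this removes the structural fault: followed literally, the plan allows a post-event test to determine subgroup membership.

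**Conclusion.** The point holds as a design fault in one secondary safety subgroup. Membership of a tested class is not fixed at time zero, and the class of untested women is undefined. If relapse prompts testing, iDFS and BCFI event rates in the tested classes are inflated.

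It would be tempting to conclude that the analysis is biased towards stimulation looking safe. The documents do not support that. It requires relapse-driven testing and also fewer non-stimulated than stimulated women tested at diagnosis. Equal testing leaves the contrast unbiased, and a reversed imbalance makes stimulation look harmful.

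Under the assumed inputs the distortion at a 20-point testing gap is about 12-19% below, or 14-23% above, a true hazard ratio of 1. In this study that rests on one or two non-stimulated carriers, or fewer than one in the stimulated cohort if the gap is reversed. The primary endpoint is unaffected. The efficacy BRCA subgroup is not exposed in the same way, because oocytes are counted before any relapse. The reason to act is that the plan leaves an avoidable, outcome-dependent choice to the analyst and the repair is cheap.

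**What to change.** In Section 5, define the BRCA safety subgroup in one of two ways:
- from tests dated on or before inclusion, with follow-up from inclusion as now; or
- from tests dated by a fixed early landmark, with follow-up counted from that landmark and only women event-free at it included. Allowing a window after inclusion without moving time zero would give women tested in the window guaranteed event-free time.

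Use three classes: mutated, tested and not mutated, and not tested by then. Do not reclassify women on later tests. An analysis using tests of any date can be kept as a sensitivity analysis, labelled as such. Report the share tested by the cut-off in each cohort, so that the reader can judge how far testing differed.

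The cost is a few sentences; the test date is already collected. The downside is that a few late-tested carriers leave the mutated class, and a landmark drops early events.
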